8. HUMAN SUBJECTS RESEARCH

8.1. PROTECTION OF HUMAN SUBJECTS

This study will be conducted in accordance with the International Conference on Harmonization Good Clinical Practice (ICH GCP) and applicable regulatory requirements. The study will be conducted in compliance with the protocol and any amendments.

The rights, safety and well-being of the patients are the most important considerations and should prevail over interests of scientists and society.

Study personnel will have requisite education, training and experience for their assigned roles including training in the ethical conduct of research.

8.2. RISKS AND BENEFITS

8.2.1. Metformin Risks

Metformin, which received FDA approval in 1995 as an oral agent to treat diabetes mellitus Type II, has been one of the most prescribed medications for this indication world-wide. Its side-effect profile is well established and it is generally safe, with several common, less serious side-effects and a few rare but very serious side-effects.

The most common side effects associated with metformin therapy include diarrhea, nausea, vomiting, abdominal discomfort as well as headache, weakness, muscle pain. Gastrointestinal symptoms are usually time limited. In the METS study, most GI symptoms resolved completely within the first week of treatment. If diarrhea or vomiting occurs, the usual approach is to hold study medication until symptoms resolve and then restart one capsule daily and titrate as tolerated.

A rare but very serious side-effect is lactic acidosis. The incidence is about 3 cases in 100,000 patient-years, with about 50% mortality when it occurs. Lactic acidosis is characterized by elevated blood lactate levels (>5 mmol/L), low blood pH, increased anion gap, and increased lactate to pyruvate ratio. When metformin is implicated, elevated metformin levels (>5 micrograms/mL) are usually found. Symptoms of lactic acidosis are generally non-specific and include weakness, somnolence, myalgia, dyspnea, dizziness, syncope, hypotension, bradycardia, hypothermia. Lactic acidosis primarily occurs in diabetic patients with renal insufficiency and in the setting of multiple serious medical and surgical conditions. Lactic acidosis also occurs in patients with congestive heart failure. The risk of lactic acidosis increases with age and degree of renal dysfunction and the risk may therefore be reduced by regular monitoring of renal function.

Metformin should not be administered to patients with impaired renal function, defined by serum creatinine levels ≥ 1.5 in males and ≥ 1.4 in females. During ongoing treatment, hematologic parameters and renal function should be measured at least annually. Metformin should not be administered to patients with hypoxemia, dehydration or sepsis. Metformin should also be avoided in patients with impaired hepatic function because of reduced lactate clearance. Alcohol potentiates the effects of metformin on lactate metabolism and therefore patients with alcohol abuse or dependence should not receive metformin. Iodinated intravascular contrast material can lower renal clearance acutely and metformin should be discontinued temporarily in anticipation of

such procedures. If patients are suspected of having lactic acidosis, it represents a medical emergency and must be treated in a hospital setting.

While metformin is not a hypoglycemic agent under usual circumstances, hypoglycemia can occur in settings of deficient caloric intake, strenuous exercise without adequate compensatory caloric intake, concomitant use of hypoglycemic agents or alcohol.

Metformin can cause reduced serum levels of vitamin B12 in <10% of patients by an unclear mechanism. This has only rarely been associated with anemia and it has been rapidly reversible with vitamin B12 supplementation or metformin discontinuation.

Drug-drug interactions are possible with metformin. In particular, oral hypoglycemic agents can potentiate a hypoglycemic state. However, patients in this study cannot have diabetes mellitus or be receiving treatment with a glucose-lower agent. Furosemide can increase blood metformin levels as can nifedipine. Cimetidine has been shown to increase metformin blood levels substantially and other cationic drugs are theoretically liable to increase levels, such as amiloride, digoxin, morphine, procainamide, quinidine, ranitidine, triamterene, trimethoprim, and vancomycin.

Metformin is rated in the Pregnancy Category B for teratogenic effects. Metformin has not been found teratogenic in rats and rabbits up to 600 mg/kg/day. Well-controlled safety data in humans is not available. Females in this study must not be pregnant and must agree to use medically acceptable contraception or abstinence during the study. If they become pregnant during the study they will be discontinued.

In addition, blood draws will be done at specified visits. There may be temporary discomfort when blood samples are taken and there is a small risk of bruising, infection or inflammation at the needle stick site. Some people may feel faint or dizzy after giving only a small amount of blood. We will use routine blood draw procedures (e.g. sterile technique) to minimize risk of the blood draw.

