3.2.1. Inclusion Criteria

1. Outpatients with a diagnosis of schizophrenia or schizoaffective disorder as defined by DSM-IV-TR criteria (see Appendix 3 and Appendix 4) and confirmed by the Structured Clinical Interview for DSM-IV (SCID).
2. Duration of psychotic illness must be greater than one year, as defined by having initiated antipsychotic treatment at least 1 year prior to study enrollment.
3. Patients must be 18-65 years of age.
4. Patients must demonstrate adequate decisional capacity to make a choice about participating in this research study and must provide written informed consent to participate.
5. BMI ≥ 27 kg/m²
6. Currently treated with one or a combination of two FDA-approved antipsychotic medications (typical or atypical antipsychotics) AND on that drug regimen for at least 2 months prior to study entry (with stable dosages for at least 1 month).
7. Concomitant medications are allowed if agents and doses are unchanged for at least 1 month prior to study entry and if these medications are not among those excluded in the Exclusion Criteria.
8. Women who can become pregnant must be using an adequate method of contraception to avoid pregnancy throughout the study and for up to 4 weeks after the study in such a manner that the risk of pregnancy is minimized. Acceptable methods include oral, injectable

or implanted contraceptives, intrauterine devices or barrier methods such as condoms, diaphragm and spermicides. Women who can become pregnant must have a negative serum pregnancy test at the Screening Visit.

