3.2.2. Exclusion Criteria

1. Inpatient status
2. Clinical Global Impression Severity (CGI-S) score ≥ 6
3. Current treatment with more than 2 antipsychotics
4. HbA1c $\geq 6.5\%$
5. Diagnosis of diabetes mellitus or current treatment with insulin or oral hypoglycemics
6. Current or prior treatment with metformin within the past 3 months
7. Current or prior treatment with lorcaserin within the past 3 months
8. Current or prior treatment with a 5-HT_{2B} agonist (e.g. cabergoline) within the past 45 days due to potential risk for heart valve defects
9. Current treatment with two or more antidepressants
10. Current treatment with a single antidepressant prescribed in excess of the maximum approved dose
11. Current treatment with monoamine oxidase inhibitor (MAOI) class of antidepressants (isocarboxazid, phenelzine, selegiline, tranylcypromine)
12. Concurrent treatment with any of the following pro-serotonergic drugs: meperidine, buspirone, dextromethorphan, triptans, tramadol, ritonavir, tryptophan, ginseng, St. John's wort
13. Diagnosis of congestive heart failure
14. Uncorrected thyroid disorder
15. Renal impairment as evidenced by estimated glomerular filtration rate (eGFR) < 50 mL/min/1.73 m²
16. Hepatic disease (ALT, AST, or GGT > 2 times upper limit of normal (ULN), total bilirubin > 1.2 times ULN)
17. Metabolic acidosis (serum CO₂ < 20 mEq/L)
18. Known hypersensitivity to metformin or lorcaserin
19. Women who are pregnant or breastfeeding
20. Recent (in the past 30 days) or scheduled radiological studies involving iodinated contrast material
21. Alcohol abuse/dependence as determined by SCID within the past month
22. Other serious and unstable medical condition in the judgment of the investigator
23. DSM-IV diagnosis of mental retardation or dementia
24. Any medication (prescription or non-prescription) used for weight loss must have been discontinued 3 months prior to study entry.

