3.5.5. Discontinuation from Study Treatment

Study treatment MUST be immediately discontinued for the following reasons:

- Withdrawal of informed consent (subject's decision to withdraw for any reason) or if patient loses the ability to provide continued informed consent in the study
- Any clinical adverse event, clinical rating, laboratory abnormality or intercurrent illness which, in the opinion of the investigator, indicates that continued treatment with study therapy is not in the best interest of the subject
- Pregnancy
- Termination of the study

Study treatment must be reevaluated for the following reason:

- Brief Psychiatric Rating Scale total score increase by $\geq 20\%$ compared to baseline will trigger a clinical evaluation to include the site's PI. This may include the subject's regular mental health provider, as needed.

Pre-specified Discontinuation Criteria:

- 1) Subject has gained >7 kg compared to baseline weight (V0) at any visit
- 2) Subject is unwilling to continue taking study drug for any reason
- 3) Clinical Global Impression-Severity scale (CGI-S) score ≥ 6 or worsening of CGI-S score by ≥ 2 points compared to baseline
- 4) Evidence for new onset suicidal ideation, plan or evidence of self-harm based on Columbia Suicide Severity Rating Scale (C-SSRS)

- 5) eGFR <45 mL/min/1.73 m²
- 6) ALT, AST, GGT >2.5xULN (upper limit of normal), total bilirubin >1.3xULN
- 7) Serum CO₂ <19 mEq/L
- 8) Meets criteria for alcohol abuse or dependence

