3.8.9. Visit 7 (Week 12)

This visit will include completing:

- Vital Signs, weight
- Blood draw for laboratory assessment (LFT (AST, ALT, GGT, total bilirubin), creatinine, eGFR, Lipid Profile, HbA1C, fasting glucose)
- Study Medication Dispensing
- CGI-S
- BPRS
- C-SSRS

- Substance Use Scale
- Alcohol Use Questionnaire
- Other Medications Record
- Study Medication Adherence Form
- Adverse Events Form
- Behavioral Treatments and Behavioral Treatment Adherence Forms

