8.2.3. Risk/benefit ratio

The risks associated with participation in this study include benign but relatively frequent gastrointestinal-related side-effects (e.g. diarrhea, nausea/vomiting, and flatulence) that occur early in the course of metformin treatment and usually disappear with the first week of continued treatment. A rare but very serious side-effect is lactic acidosis which occurs in about 3 in 100,000 patient years with about 50% mortality rate. While lactic acidosis is very serious, it primarily occurs in diabetic patients with renal insufficiency, in the setting of multiple serious surgical and medical conditions, including congestive heart failure, and in alcohol abuse. The risk of lactic acidosis increases with age and degree of renal dysfunction. Given these known risk factors of lactic acidosis, the risk of developing lactic acidosis in the current study is limited further by excluding any patients that have one or more of these risk factors or laboratory evidence of reduced renal function. The risk of serotonin syndrome may be increased with the use of lorcaserin. Serotonin syndrome is a rare but serious side effect that is characterized by a constellation of signs and symptoms that can include tachycardia, agitation, confusion, hypertension, rigidity, tremor, hyperpyrexia, and hyperreflexia. One probable case and one possible case of serotonin syndrome were identified among 3,400 subjects who received lorcaserin in the FDA registration trials. Targeted side effect monitoring aimed at detecting serotonin syndrome, or less fulminant serotonin excess, will be performed at each study visit. Furthermore, as part of the behavioral intervention, each subject will be contacted via telephone weekly or biweekly and subjects will also be screening for serotonin excess at those points of contact.

Participants could potentially benefit by receiving a medication treatment that, in combination with behavioral modification, is effective in reducing their weight, and could result in reduced morbidity and risk of other medical conditions. It is judged that the benefits which subjects will receive from

closely monitored treatment, in addition to the societal benefits of important treatment data concerning a disorder with substantial morbidity and mortality, reasonably outweigh the risks to participating subjects.

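### The risk section bars metformin at or above a serum creatinine limit that no entry or stopping rule applies, so the eGFR rules can admit and retain some subjects it says should not receive it

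*Combined protocol and SAP*

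**What the plan says.** Four places in the combined protocol and SAP bear on renal function.

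- Section 8.2.1 (Metformin Risks): "Metformin should not be administered to patients with impaired renal function, defined by serum creatinine levels" at or above 1.5 in men and 1.4 in women. No unit is printed.
- Section 3.2.2, exclusion 15: "Renal impairment as evidenced by estimated glomerular filtration rate (eGFR) < 50 mL/min/1.73" m².
- Section 3.5.5, pre-specified discontinuation criterion 5: "eGFR <45 mL/min/1.73" m².
- Section 8.2.3 (Risk/benefit ratio) says the risk of lactic acidosis is limited by "excluding any patients that have one or more of these risk factors or laboratory evidence of reduced renal function".

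Creatinine is measured. The Week 12 list, for example, reads "Blood draw for laboratory assessment (LFT (AST, ALT, GGT, total bilirubin), creatinine, eGFR, Lipid Profile, HbA1C, fasting glucose", and the schedules in Appendices 1 and 2 put creatinine and eGFR on one line at screening and at weeks 12, 24, 36 and 52. No inclusion, exclusion or discontinuation criterion attaches a limit to creatinine, and no eGFR equation is named.

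**The concern.** The protocol defines renal impairment twice, on two scales. eGFR depends on age and sex as well as creatinine, so a fixed creatinine limit and a fixed eGFR limit cannot select the same people across the eligible age range. A subject at or above the creatinine limit may therefore pass exclusion 15, be randomised to lorcaserin/metformin, and stay clear of discontinuation criterion 5. Section 8.2.1 says that subject should not receive metformin.

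What is at stake is the accuracy of the risk description. Section 8.2.1 ties the risk of lactic acidosis to the degree of renal dysfunction, with about 50% mortality when it occurs, and Section 8.2.3 relies on renal exclusion in its risk/benefit judgement. Someone who reads only Section 8 could believe a creatinine restriction is in force.

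**Working it through.** There is no stated figure to reproduce. The check converts the Section 8.2.1 creatinine limits to eGFR and compares the result with 50 and 45.

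**Inputs from the documents:** creatinine 1.5 (men) and 1.4 (women), Section 8.2.1; eGFR 50, Section 3.2.2; eGFR 45, Section 3.5.5; "Patients must be 18-65 years of age", Section 3.2.1.

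**Assumptions:** creatinine in mg/dL, and three common creatinine-based equations without a race term, used to show a range. At these creatinine values each reduces to a function of age:

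- MDRD (4-variable): 175 × Cr^−1.154 × age^−0.203, × 0.742 for women
- CKD-EPI 2009: 141 × (Cr/k)^−1.209 × 0.993^age, × 1.018 for women
- CKD-EPI 2021: 142 × (Cr/k)^−1.2 × 0.9938^age, × 1.012 for women

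with k = 0.9 for men and 0.7 for women.

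Example, a man aged 18 under MDRD: 175 × 1.5^−1.154 × 18^−0.203 = 61.0. At age 65 the same formula gives 47.0.

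| At the Section 8.2.1 limit | eGFR, age 18 to 65 | Passes entry (≥ 50) | Not stopped (≥ 45) |
|---|---|---|---|
| Man, 1.5, MDRD | 61.0 to 47.0 | ages 18–47 | ages 18–65 |
| Man, 1.5, CKD-EPI 2009 | 67.0 to 48.2 | ages 18–59 | ages 18–65 |
| Man, 1.5, CKD-EPI 2021 | 68.8 to 51.3 | ages 18–65 | ages 18–65 |
| Woman, 1.4, MDRD | 49.0 to 37.7 | no age | ages 18–27 |
| Woman, 1.4, CKD-EPI 2009 | 54.7 to 39.3 | ages 18–30 | ages 18–45 |
| Woman, 1.4, CKD-EPI 2021 | 55.9 to 41.8 | ages 18–36 | ages 18–52 |

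**Width of the gap.** A 40-year-old man falls to eGFR 50 at creatinine of about 1.55, 1.68 or 1.75 under the three equations in turn, and to eGFR 45 at about 1.70, 1.83 or 1.91. From 1.5 up to those values he is inside the Section 8.2.1 bar but passes the numeric entry rule or stopping rule respectively.

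**The other direction.** A 65-year-old woman falls to eGFR 50 at about 1.10, 1.15 or 1.20, well below 1.4. For her the eGFR rule is the stricter one, so neither definition contains the other.

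**Sensitivity.** Adding the race term that the first two equations can carry widens the gap. Men at 1.5 then pass entry at all ages 18–65. Women at 1.4 pass to age 41 (MDRD) or 51 (CKD-EPI 2009) and are not stopped at any age 18–65.

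**The case against.** The strongest reply is that Section 8.2.1 is general drug-risk text, not a trial rule. The sentence after the creatinine limit speaks of renal monitoring at least annually, which is not this trial's schedule, and the section uses explicit in-this-study wording elsewhere (on diabetes and pregnancy) but not here. That is a fair reading of its origin. It does not remove the conflict, because the text still says metformin should not be given and defines for whom, and nothing tells the reader that the trial uses another limit.

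Safeguards also exist. Section 3.9.10 requires the PI's permission to randomise a patient whose screening or baseline result is judged clinically significant, and promises laboratory guidelines to sites. Section 3.5.5 requires stopping for any laboratory abnormality that, in the investigator's opinion, makes continued treatment contrary to the subject's interest. These stand as mitigation, but they are discretionary and the protocol attaches no creatinine number to them.

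Section 8.2.3 names no creatinine limit, and a low eGFR is laboratory evidence of reduced renal function. Its assurance can therefore be met by exclusion 15 alone. It fails only on Section 8.2.1's definition.

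A reader might infer three stronger things that the documents do not support:

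- *Sites would enrol or stop different subjects.* Sections 3.8.2 and 3.8.3 send sites to Sections 3.2.1 and 3.2.2 for eligibility, and the stopping limits are in Section 3.5.5. No eligibility or stopping text points to Section 8.2.1, so divergence between sites is speculation.
- *The renal limit is the main protection against lactic acidosis.* No passage ranks it first. Heart failure, hepatic disease, metabolic acidosis, recent or scheduled contrast studies and alcohol abuse or dependence are also excluded.
- *The 50/45 difference is itself an error.* Other limits are paired the same way, looser for stopping than for entry: liver enzymes 2 and 2.5 × ULN, bilirubin 1.2 and 1.3 × ULN, serum CO₂ 20 and 19 mEq/L.

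**Conclusion.** The inconsistency is real and rests on the documents alone: a creatinine bar in Section 8.2.1, eGFR limits in Sections 3.2.2 and 3.5.5, and no text joining them. Under the numeric rules, some subjects whom Section 8.2.1 says should not receive metformin can be enrolled and kept on it, subject only to discretionary review.

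The extent depends on the assumed unit and equation. The result is firm for men: under all three equations they pass entry at creatinine 1.5 to at least age 47 and are not stopped at any eligible age. For women it is limited to younger ages, and under MDRD without a race term it does not arise at entry at all.

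The documents do not allow an estimate of how many subjects are affected, and only the lorcaserin/metformin arm receives metformin. No effect on the endpoint, the primary analysis or power is claimed. This is a safety threshold on which the protocol contradicts itself, and it should be corrected.

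**What to change.** Reconcile the creatinine statement in Section 8.2.1, and the assurance in Section 8.2.3, with exclusion 15 and discontinuation criterion 5, so that the renal limit described in the risk section is the one the trial applies. If eGFR is kept, name the equation; if a creatinine figure is kept, state its unit. Entry and stopping thresholds may differ. Which limits are right is a clinical decision for the sponsor, and this review takes no position on it.

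The cost is protocol wording submitted as an amendment. Creatinine and eGFR are already drawn together, so no new test or visit is needed.

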8.2.1.1. Lorcaserin Risks

Lorcaserin has a well-established and generally benign side effect profile. Trials to date that have included over 3,400 subjects exposed to lorcaserin for at least 1 year found the most common adverse events for lorcaserin compared to placebo were headache (17% vs 10%), dizziness (9% vs 4%), nausea (8% vs 5%), and fatigue (7% vs 3%). There were no differences in the occurrence of depression, anxiety or other psychiatric events, including suicidal ideation in studies of lorcaserin at lorcaserin doses up to 20 mg per day. At supratherapeutic doses from short-term Phase I safety studies in non-obese healthy volunteers, doses of 40 and 60 mg per day were associated with increased incidence of euphoria compared to placebo (up to 19% of subjects reported euphoria). In subsequent studies in obese individuals of lorcaserin up to 40 mg per day, reports of euphoria were low (<1%). In the large Phase III trials with lorcaserin limited to 20 mg per day, there was no increase in reports of euphoria or other symptoms of

mania, psychosis or physical/psychological dependence compared to placebo (Smith et al., 2010; Fidler et al., 2011). Because of the potential for lorcaserin to cause euphoria at suprathreshold doses, it has been listed as a Schedule IV controlled substance. There are no data from animal or human studies demonstrating whether lorcaserin can induce physical dependence.

Lorcaserin has not previously been studied in people with schizophrenia. However, 5-HT_{2C} agonists have previously been hypothesized to have potential antipsychotic efficacy by reducing mesocortical dopamine transmission in animal models of psychosis. To test this hypothesis, a recent 6 week RCT examined the safety and efficacy of vabicaserin, a selective 5-HT_{2C} agonist versus olanzapine in 289 people with acutely exacerbated schizophrenia. Vabicaserin was found to produce similar improvements to olanzapine in positive psychotic symptoms, with no benefits on negative symptoms. There was no evidence of significant side effects associated with vabicaserin, including no evidence of psychotic exacerbation or exacerbation of other psychiatric symptoms (Shen et al, 2014). Although not directly testing lorcaserin, these data provide reassurance that 5-HT_{2C} agonists do not pose a significant risk of psychotic exacerbation in people with schizophrenia, and that 5-HT_{2C} agonists as a class may actually exert a therapeutic role for psychosis.

Given that lorcaserin is a serotonin receptor agonist, it has a potential risk of causing side effects associated with serotonin excess including the possible risk of serotonin syndrome. Serotonin syndrome is a rare but serious side effect that is characterized by a constellation of signs and symptoms that can include tachycardia, agitation, confusion, hypertension, rigidity, tremor, hyperpyrexia, and hyperreflexia (Boyer et al. 2005). It has been associated with agonism at the 5HT_{2A} receptor (Nisijima et al, 2001; Isbister et al., 2001) and usually resolves quite rapidly following administration of a 5HT_{2A} antagonist such as cyproheptadine. Because lorcaserin is a 5HT_{2C} agonist, it does not normally induce serotonin syndrome. However, one of the 3,400 subjects exposed to lorcaserin in the registration trials developed symptoms consistent with moderate severity serotonin syndrome, and one subject developed mild symptoms judged possibly consistent with serotonin syndrome. Given that lorcaserin has not previously been studied in people with psychosis or depression, the safety of co-administration of other serotonergic agents has not been well established. The current study will take precautions by excluding patients taking pro-serotonergic agents including meperidine, buspirone, dextromethorphan, triptans, tramadol, ritonavir, tryptophan, ginseng, St. John's wort. The current project provides an excellent opportunity to begin to collect data on the tolerability and safety of lorcaserin in clinically stable patients with schizophrenia taking antipsychotics. Subjects will be instructed in the signs and symptoms of serotonin syndrome and instructed to contact the research clinic or to seek emergency medical care. Side-effect monitoring aimed at psychiatric decompensation using the BPRS, C-SSRS and CGI will be administered regularly, especially during the first 3 months of the trial. Targeted side effect monitoring aimed at detecting serotonin

syndrome, or less fulminant serotonin excess, will be performed at each study visit. Furthermore, as part of the behavioral intervention, each subject will be contacted via telephone each week of the study to review the last behavioral lesson, and during these calls, subjects will be screened for evidence of serotonin syndrome.

A prior concern with non-selective serotonin agonists for weight loss (e.g. fenfluramine, dexfenfluramine) had been cardiac valvulopathy, which led to the withdrawal of these agents by the FDA. The mechanism underlying valvular heart disease has been traced to agonism at 5-HT_{2B} receptors which are expressed on cardiac valves (Rothman et al., 2000; Roth, 2007). As a selective 5-HT_{2C} agonist, lorcaserin is not expected to produce similar cardiac valve problems and this was confirmed in the BLOOM and BLOSSOM studies (Smith et al., 2010; Fidler et al., 2011). Echocardiography was conducted on all participants and no evidence of lorcaserin-associated valvulopathy emerged.

Finally, the BLOOM-DM study demonstrated the safety of concurrent treatment with lorcaserin and metformin (O'Neil et al., 2012). Of the 604 enrolled participants, over 90% were taking stable doses of metformin at study entry. There were no significant safety signals that emerged, including similar rates of reported hypoglycemia between lorcaserin 10 mg BID (7.4%) and placebo (6.3%) arms.

